If the physician determines that the patient is a candidate for the FR program and the patient is willing to commit to this intensive treatment approach, the patient is evaluated by a physical therapist to measure baseline functional status and to determine if he/she has the physical stamina to successfully participate in FR.

The research coordinator or research assistant will perform a brief screen of each potential subject's medical record to determine if he/she has any excluding conditions. If the potential subject has no excluding conditions, the research coordinator or research assistant will meet with him/her to explain the study and to request their consent for study participation. The commanding officer for each subject will be contacted and asked to approve the subject's absence from work as needed for the 6-9 week program.

Randomization

Then, each patient will be randomized to one of two treatment groups: the standard FR program or the FR + integrative modalities (IM) program. Because it is assumed that some participants who randomize to the standard FR program may be interested in IM, the standard FR group will be offered the option of IM following completion of the FR program. The components of the intervention and control treatments are shown in Table 2.

Standard care is comprised of twice weekly health psychology group therapy, twice weekly physical therapy and once-twice weekly occupational therapy during the three weeks prior to FR. Participants on chronic opioid therapy will also be seen by a clinical pharmacist for evaluation for opioid taper. The IM program is comprised of twice weekly acupuncture and chiropractic and once weekly yoga and myofascial release instruction by massage therapist. If indicated, biofeedback and individual massage may also be used. The FR program includes four full days of therapy per week for three weeks. Each FR treatment day will include approximately four-hours of physical activity and one hour each per day of health psychology group therapy and an educational session. Examples of the daily schedules for SC, IM and FR is shown in Figure 2. In an effort to meet enrollment targets, patients who are otherwise eligible for FR program participation but cannot commit to 4 full days of therapy for a three-week period will be given the option of 2 full days of therapy over a six-week period for the same number of contact hours.

Table 2. Intervention and Standard Care

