Patient demographic data and patient-reported outcomes will be collected using the DOD's Pain Assessment Screening Tool and Outcomes Registry (PASTOR).⁶² This Web-based patient-reported outcomes tool, currently used at Madigan IPMC,⁶³ was designed to reduce the burden of patient questionnaires during clinical contact through modern information technology and to make use of **well-established and validated pain-related assessments** already available. It uses the computerized adaptive learning system of the Patient Reported Outcome Measurement Information System (PROMIS), which contains a large, validated databank of all surveys from the literature and was developed by the National Institutes of Health (NIH). Notably, PASTOR is one of the major recommendations from the 2010 Army Pain Management Task Force Report. PASTOR will serve two major purposes: first, it will collect longitudinal outcomes data on patients treated in military hospitals in an outcomes registry; and second, it will provide a summary outcomes report on each patient for the IM and FR clinical team for review at during each assessment period. The PASTOR outcomes report (which includes the specific outcomes and treatment data collected) is presented in Section 6: Surveys, Questionnaires, and Other Data Collection Instruments – PASTOR. It is currently beginning a beta-test phase in select Army and Navy medical treatment facilities (including MAMC), and will be implemented during 2015-16 as standard of care for pain assessment at Army hospitals nationwide.

All patients will complete scheduled assessments according to the following timeline of the study:

1. At baseline, prior to randomization to SC or IM
2. At completion of SC or IM, prior to initiation of FR program
3. At completion of FR program

4. At 3-months post-FR program

5. At 6-months post-FR program

Table 3. Patient-Reported Outcome Measures in PASTOR

Primary Outcomes

Defense and Veterans Pain Rating Scale (DVPRS)⁶⁴

- Pain Intensity 10-pt Numeric Rating Scale (NRS)

Physical Function Subscale of PROMIS Global Health⁶⁵

Secondary Outcomes

PROMIS Pain Interference⁶⁶

PROMIS Depression⁶⁷

PROMIS Anxiety⁶⁷

PROMIS Emotional Distress - Anger⁶⁷

PROMIS Sleep Disturbance⁶⁸

PROMIS Fatigue⁶⁹

Patient-defined activity goal⁷⁰

Patient Activation Measure (PAM)⁷¹

Drug Use Questionnaire (DAST-10)⁷²

Pain Catastrophizing Scale (PCS)⁷³

Tampa Scale for Kinesiophobia (TSK11)⁷⁴

Pain Self Efficacy Questionnaire (PSEQ)⁷⁵

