The individual validated scales and clinical screening tools in PASTOR are summarized in Table 3. **Pain intensity** will be rated on a 0 – 10 scale (0 = no pain, 10 = worst possible pain). All PROMIS measures are administered using computerized adaptive testing, thus ensuring a low response burden to the patient. The recall period is 7 days. The PROMIS **pain interference** item bank specifically focuses not on the more commonly measured pain intensity, but on pain interference, defined as interference of pain in daily activities involving physical, psychological, and social functioning. The PROMIS **depressive symptoms** consist of items that address sadness, loss of interest, worthlessness, low self-esteem, loneliness, and interpersonal alienation. The PROMIS **anxiety** consists of an item bank that addresses fearfulness, worry, and nervousness. The PROMIS **emotional distress – anger** item bank assesses angry mood, negative social cognitions, verbal aggression, and efforts to control anger. The PROMIS **global health** item pool assesses health in general. The global health items include global ratings of the five primary PROMIS domains, physical function, fatigue, pain, emotional distress, social health, as well as perceptions of general health that cut across domains. The PROMIS **sleep disturbance** item bank assess perceptions of sleep quality, sleep depth, and restoration associated with sleep; perceived difficulties and concerns with getting to sleep or staying asleep; and perceptions of the adequacy of and

satisfaction with sleep. The PROMIS **fatigue** consists of items that address fatigue from mild subjective feelings of tiredness to overwhelming and sustained sense of exhaustion. PASTOR also includes 11 items related to prior and current treatment modalities; 5 items asking about health care utilization and a 3 item opioid utilization screener.

Supplemental Assessments

PASTOR also includes a battery of supplemental assessments that are relevant for screening and monitoring patient outcomes on several other domains of importance to patients enrolled in a functional restoration program.

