During the course of the study, a protocol modification was approved to allow subjects to participate in the FR program with an extended 2 days per week over 6 week schedule with the same number of treatment hours as the original 4 days per week for 3 weeks. We will evaluate outcomes in both groups to determine if one treatment approach yielded superior outcomes to the other.

Analytical Technique: We will use a Sequential Multiple Regression model.⁷⁹ We will assess the relative importance of the FR delivery method (either 4 days per week x 3 weeks vs. 2 days per week x 6 weeks controlling for treatment group on our primary outcomes of pain and physical function as well as on the secondary outcomes measures (depression, anxiety, anger, sleep quality, fatigue, medical board status for disability, duration of pain-related disability, prescription opioid dosage, and functional capacity tests for endurance and strength).

Aim 6: Compare outcome measures collected within narrow timelines to those collected within flexible timelines.

We attempted to collect outcome measures at the following timepoints: 1) within one month before starting treatment; 2) within the last day of pre-FR stage through the first day of FR stage; 3) on the last day of FR; 4) 3- and 5) 6- months after the end of FR. However, this precise collection schedule was not always possible. For example, baseline measures were collected more than one month before the start of treatment for study subjects who had conflicts such as military training exercises, personal or family illness or planned leisure travel which postponed the start of study treatment. Collection of follow-up measures was sometimes earlier or later than desired when study subjects with conflicts were unavailable at the time outcomes were requested. We plan to compare outcomes collected within the above timeframes with those collected within timeframes with modest and moderate flexibility as outlined in the following table. This analysis will inform the design of future pragmatic clinical trials in determining acceptable timeline parameters for collection of pain outcomes.

	Baseline	End of pre-FR stage	End of FR stage	Short-term	Intermediate-term
Narrow timelines	w/in 1 month of treatment start	Last day of pre-FR up to start of FR	Last day of FR	3 months after end of FR	6 months after end of FR

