Modest flexibility	w/in 2 months of treatment start	\leq 2 treatment days before end of pre-FR, through \leq 2 treatment days after start of FR	\leq 2 treatment days before end of FR, through \leq 7 calendar days after end of FR	2-4 months after end of FR	5-7 months after end of FR
Moderate flexibility	w/in 3 months of treatment start thru 2 days after treatment start	\leq 2 treatment days before end of pre-FR, through \leq 4 treatment days after start of FR	\leq 2 treatment days before end of FR, through \leq 30 calendar days after end of FR	1-<5 months after end of FR	6-9 months after end of FR

Analytical Technique: We will use a Sequential Multiple Regression model.⁷⁹ We will assess the relative importance of the timing of assessments on our primary outcomes of pain and physical function as well as on the secondary outcomes measures (pain interference, depression, anxiety, anger, sleep quality, fatigue, medical board status for disability, duration of pain-related disability, prescription opioid dosage, and functional capacity tests for endurance and strength). We will code an indicator variable to document every observation that occurs within the narrow timeline. We will use an interaction term of this indicator with the intervention to see if the intervention shows a differential effect for those who adhere to the narrow assessment timelines.

Aim 7: Determine if patient activation, pain catastrophizing, self-efficacy or pain acceptance moderate or mediates pain and function outcomes.

We will determine if level of patient activation, catastrophizing, self-efficacy and pain acceptance as measured by legacy questionnaires completed by study subjects have an impact on pain and functional outcomes.

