Describe the plan to address incidental findings and unexpected findings about individuals from screening to the end of the subject's participation in the research. In cases where the subject could possibly benefit medically or otherwise from the information, state whether or not the results of screening, research participation, research tests, etc., will be shared with subjects or their primary care provider. State whether the researcher is obligated or mandated to report results to appropriate military or civilian authorities and explain the potential impact on the subject

The study is low-risk; therefore we do not anticipate any serious adverse events.

The most likely adverse event associated with participation in this study is mild-self-limited muscular soreness in the initial days of functional restoration, as each participant begins the reconditioning process. This is anticipated to occur in 75% of participants and to resolve within one week of onset. These complaints will be addressed and managed by the IPMC physical and occupational therapy teams.

This intervention qualifies as a Phase II clinical trial. We have developed a data and safety monitoring plan, which is outlined below. The plan includes routine monitoring of adverse events by the PI and study staff.

Monitoring study safety. Study safety will be monitored quarterly and includes auditing a random selection of 5% of cases for compliance with IRB requirements, conformance with informed consent requirements, verification of source documents and investigator compliance. Conference calls or in-person meetings are scheduled quarterly or on an as-needed basis with all data collectors and providers to review protocol and possible study safety issues. Booster sessions on administering the protocols will be given if needed. Each study team member will also receive a personal performance update with comments on protocol adherence and completeness of data. All violations of protocol are noted.

Identification of Adverse Events. [name] will be responsible for monitoring the internal review of adverse events. Adverse events will be identified by either intervention facilitators or study staff and reported to either [name] within 72 hours of occurrence, who will determine whether the event qualifies for reporting to the IRB.

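### Aim 6 accepts end-of-pre-FR scores taken up to 4 treatment days into FR, and its single narrow/not-narrow code cannot separate them from scores taken early

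*Combined protocol and SAP*

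**What the plan says.** Section 10.1 (Patient-Reported Outcomes) lists the second assessment as "At completion of SC or IM, prior to initiation of FR program". The Design paragraph of the same section also puts it between the end of pre-FR treatment and the start of FR.

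The Aim 6 timeline table in section 11.3 has three tiers for this time point:

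- Narrow: "Last day of pre-FR up to start of FR".
- Modest: from 2 treatment days before the end of pre-FR to "2 treatment days after start of FR".
- Moderate: the same early limit, and a late limit of "4 treatment days after start of FR".

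The Aim 6 text (sections 9.4 and 11.3) differs slightly from the table. It lets the target window run to include the first FR day.

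The Aim 6 analysis codes one indicator for whether an observation falls in the narrow window, and tests its interaction with the intervention. It has no term for whether FR had begun or for how many FR days had been received.

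Three other statements bear on this. Section 10.2 says, directly after describing the PROMIS measures, "The recall period is 7 days". Section 14.6 expects "mild-self-limited muscular soreness in the initial days of functional restoration" and adds: "This is anticipated to occur in 75% of participants and to resolve within one week of onset". Section 10.1 sets FR at four days a week for three weeks, and patients who cannot commit to that "will be given the option of 2 full days of therapy over a six-week period for the same number of contact hours".

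**The concern.** The second assessment is the only post-baseline measurement that can show integrative modalities (IM) against standard care (SC) without FR. A score taken after several FR sessions reflects a different treatment stage, whatever the column is called. The plan itself expects most participants to be sore early in FR, and early benefit from FR could move scores the other way.

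Aim 6 is meant to advise future pragmatic trials on how much slack in collection times is tolerable. That requires timing to vary while treatment stage stays the same. On the late side of this window both change together, and the single indicator then pools late scores with early ones. A difference between narrow and non-narrow scores could come from having started FR. Equally, no difference could mean that opposing effects cancelled, and late collection would look harmless.

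Aim 1 has a hypothesis about the arms on entry to FR, and the plan does not say which window defines that time point.

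**Working it through.** No stated sample size, power or alpha figure bears on this point, so there is none to reproduce. The check is how much FR exposure and how much in-FR recall the windows allow.

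**Inputs from the documents**

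- Late limits of 2 and 4 treatment days (section 11.3, Aim 6 table).
- Recall of 7 days (section 10.2).
- FR treatment days: 4 × 3 = 12 on the three-week schedule and 2 × 6 = 12 on the six-week schedule (section 10.1).

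**Assumptions**

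- FR sessions fall on a fixed weekday pattern, Monday to Friday, starting with the first day of the pattern. All such patterns were enumerated.
- The table does not say whether the first FR day counts towards the limit, so both rules are shown. The limit of k is either the k-th treatment day or the k-th after the first.
- The recall period either ends on the assessment day or covers the 7 days before it.

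**Formula**

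Let d be the calendar day of FR at the limit, with the first FR day as day 1. Recall days inside FR are min(7, d) if the assessment day is included and min(7, d − 1) if it is not. The recall ranges below span both rules. FR days given include the assessment day.

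| Schedule | Limit | First FR day counted? | FR calendar day | Recall days inside FR | FR days given |
|---|---|---|---|---|---|
| 4 days/week | 2 | yes | 2–3 | 1–3 of 7 | 2 of 12 |
| 4 days/week | 2 | no | 3–4 | 2–4 of 7 | 3 of 12 |
| 4 days/week | 4 | yes | 4–5 | 3–5 of 7 | 4 of 12 |
| 4 days/week | 4 | no | 8 | 7 of 7 | 5 of 12 |
| 2 days/week | 2 | yes | 2–5 | 1–5 of 7 | 2 of 12 |
| 2 days/week | 2 | no | 8 | 7 of 7 | 3 of 12 |
| 2 days/week | 4 | yes | 9–12 | 7 of 7 | 4 of 12 |
| 2 days/week | 4 | no | 15 | 7 of 7 | 5 of 12 |

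At the moderate limit the share of FR given is 4/12 = 33% or 5/12 = 42%. On the 2-day schedule no recall day precedes FR under any rule. On the 4-day schedule that depends on the counting rule.

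For comparison, a score taken 2 treatment days before the end of pre-FR has 0 of 7 recall days inside FR. Under the planned indicator it has the same code, not narrow, as a score with 7 of 7.

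A score on the first FR day has no settled code. It is narrow by the Aim 6 text, but not by the table if the start of FR means the first session.

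**The case against.** The strongest reply is that these windows belong to Aim 6 alone. The plan reports that exact timing was not always achieved and sorts scores by how far they missed the target. Late scores are what Aim 6 sets out to study, and closing the flexible tiers at the first FR session would remove them. It would also be stricter than the target in the Aim 6 text. This stands as a reason to keep the late scores and code them properly. It does not justify pooling them with early scores.

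Several stronger readings are tempting, and the documents do not support them:

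- **That narrow versus flexible is simply before FR versus during FR.** Both flexible tiers also admit scores from before the end of pre-FR, so the non-narrow group is a mixture.
- **That Aim 1 is contaminated.** Nothing says the flexible tiers feed Aim 1. Both arms go on to FR, so soreness common to both need not bias IM against SC unless lateness or the response to early FR differs by arm. Change from baseline would still be distorted by any late scores used.
- **That soreness shifts late scores by a known amount.** The plan gives a frequency but no effect on the pain scale, and no share of scores that are late. It calls the soreness mild and short-lived, so by days 9 to 15 on the 2-day schedule it may have faded. The score would still be an in-FR score.
- **That all late scores recall only FR time.** This is a result at the limit. On the 4-day schedule it needs the first FR day to be left uncounted. The 7-day recall is clear for PROMIS but not for the 0–10 pain item, although a rating of current pain would still be made during FR.

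**Conclusion.** The point holds as a fault in how Aim 6 defines and codes this time point. The protocol's own definition and the table's late limits disagree, and one indicator cannot separate treatment stage from timing tolerance.

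The size is what the exposure figures show: at the moderate limit a third or more of FR has been given, and the PROMIS recall can contain no pre-FR time. Because the limit is counted in treatment days, the same tier also covers different calendar time on the two FR schedules. These figures rest on the fixed weekday pattern and the two counting rules. No shift in outcome points is claimed, because the documents give no basis for one.

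The primary analysis is at 3 months and is not directly affected. The exposed results are the Aim 6 comparison at the second assessment and, only if late scores are used there, the Aim 1 contrast on entry to FR.

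**What to change.** 1. Flag each second-assessment score as taken before or after the first FR session. Section 10.12 already lists FR start dates among the recorded data. Those are dates, so add a rule for scores dated on the first FR day.
2. In Aim 6, replace the single indicator at this time point with separate terms for early scores and for post-FR-start scores. Include the number of FR days received, so that the two schedules are comparable. State whether the first FR day counts towards the limits.
3. In Aim 1, do not use scores taken after the first FR session as the pre-FR time point, or show the result with and without them. State which window Aim 1 uses.
4. Reconcile the Aim 6 text, which includes the first FR day in the target window, with the table, which stops at the start of FR.

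The cost is a recoding rule, one or two extra model terms and a few more missing pre-FR values in Aim 1. The planned hierarchical model can accommodate those values under the missing-at-random assumption stated in section 11.3. No new data collection is needed for the flag beyond resolving same-day scores.

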A comparative effectiveness study, using a prospective randomized cohort design, with patients assigned to either (i) a course of integrative pain management modalities (IM) or (ii) standard care (SC), for three weeks prior to beginning a course of FR. Upon completion of the pre-FR treatment arms, all patients will be enrolled into the FR program for the duration of three weeks (up to 96 contact hours; 4 full day session/week). Because it is anticipated that some participants who randomize to the standard FR program may be interested in IM, the standard FR group will be offered the option of IM following completion of the FR program. Outcomes will be collected longitudinally at several time points during the course of the study, including at: (i) baseline, prior to initiation of treatment arms; (ii) completion of pre-FR treatment, before initiation of FR program; (iii) completion of FR program; (iv) 3-months, and 6-months post-FR. Figure 1 illustrates the study design and the multiple points of outcomes assessment throughout the study.

Project Timeline

Acronyms: IM (Integrative Modalities): Acupuncture, Chiropractic, Massage, Biofeedback + SC
SC (Standard Care): PT/OT 2-3 hrs/week; CBT 2 hrs/week; +/- clinical pharm x 3 wks
FR (Functional Restoration): PT/OT 4 hrs/day; CBT 1 hr/day; 4 days/week x 3 wks
PASTOR (Pain Assessment Screen Tool and Outcomes Registry)
PROMIS (Patient Reported Outcomes Measurement Information System)
MED (Morphine Equivalent Dose)
PT (Physical Therapy); OT (Occupational Therapy); CBT (Cognitive Behav Therapy)

Procedures

Recruitment

All military personnel referred to the Madigan Interdisciplinary Pain Management Clinic have an initial 30-minute orientation group class with a nurse case manager (NCM) who provides an overview of interdisciplinary pain care. At the conclusion of this class, all new patients are provided a laptop computer and instructed to complete the baseline Pain Assessment Screening Tool and Outcomes Registry (PASTOR) questionnaire. Immediately following the IPMC orientation class, all new patients have a 90-minute introduction to the role of cognitive behavioral therapy in pain care. Within the following two weeks, each patient has an initial comprehensive visit with a physician to determine the pain diagnosis and treatment plan.

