	Approximate Contact hours	Intervention Group	Control Group
Standard Pre-FR Care (SC)			
CBT 90-minute orientation	90-minutes	X	X
Health psychology / CBT group therapy	2 hrs/wk x 3 weeks	X	X
Physical therapy/occupational therapy warm-up	2-3 hrs/wk x 3 weeks	X	X
Clinical pharmacist evaluation (if taking opioids)	1-2 hours during 3 weeks	X	X
IM prior to FR:	3 weeks comprised of:		
Chiropractic	15-minutes, twice per week	X	
Acupuncture	1-hr, twice per week	X	
Yoga	1-hr per week	X	
Biofeedback (if indicated)	45-min per week	X	

Foam roller class	1-hr per week	X	
Medical massage (if indicated)	1-hr every other week		
FR program:	3 weeks comprised of: Physical training Health psychology/CBT group therapy Didactic education	X X X	X X X
	4-hrs per day, 4 days per week 1-hr per day, 4 days per week 1-hr per day, 4 days per week -or- 6 weeks comprised of: 4-hrs per day, 2 days per week 1-hr per day, 4 days per week 1-hr per day, 4 days per week	X X X X X	X X X
IM after FR:	3 weeks comprised of: Chiropractic Acupuncture Yoga Biofeedback (if indicated) Foam roller class Medical massage (if indicated)	15-minutes, twice per week 1-hr, twice per week 1-hr per week 45-min per week 1-hr per week 1-hr every other week	X (patient option) X (patient option) X (patient option) X (patient option) X (patient option) X (patient option) X (patient option)

Patient-Reported Outcomes

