- N/A – will not use or disclose protected health information (PHI)
- HIPAA Authorization will be obtained
- Use of a limited data set where a data use agreement will be obtained
- Waiver/alteration of HIPAA Authorization is being requested

10.12 Managing Data (Data Management and/or Sharing Plan) and/or Human Biological Specimens for this Study:

Include in this section the plan for acquiring data (both electronic and hard copy), access during the study, data/specimen storage and length of time stored, shipment/transmission, and the plan for storage and final disposition at the conclusion of the study. Describe any data agreements in place for accessing data within and/or outside of your institution (e.g., Data Sharing Agreement, Data Use Agreement, Business Agreements, etc.)

The following is an explanation of how study data will be managed.

1. Master Key. Will include information on the name, date of birth and Social Security number for each study subject and documentation that each is a suitable study subject based on inclusion /exclusion criteria. These data will be maintain in an excel spreadsheet on a secure, password-protected server.
2. Subject data sheets. Will include each study subjects study ID number, their age, military rank, military occupational specialty (MOS), military unit, date consent obtained, result of randomization, starting and ending dates of participation in standard care, integrative modalities care and functional restoration and functional outcome measures (floor-knuckle lift test; knuckle-shoulder lift test, 40-foot carry test and Naughton treadmill test). Final data analysis of this de-identified data will be done at the University of Washington.

3. Informed consent forms. Will be stored in a locked file cabinet at Madigan Army Medical Center (MAMC) in the office of the study administrative staff.
4. PASTOR data. Study subjects will complete PASTOR electronic questionnaires periodically during the study period. PASTOR is managed by the Army Analytics Group (AAG). PASTOR data for study subjects will be transferred using AMRDEC to the Defense Health Agency Solution Delivery Division (DHA/SDD) to be merged with data compiled by DHA/SDD (and explained in #10 below). Patients will have access to their responses and the trends of those responses over time. All Interdisciplinary Pain Management Clinic (IPMC) providers and primary care providers involved in the care of these patients will have access to PASTOR results.

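### At the end-of-FR time point, the flexible windows in Aim 6 admit control scores taken after optional post-FR IM has begun, so the timing-by-arm interaction partly confounds timing with crossover

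*Combined protocol and SAP*

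**What the plan says.** Section 11.3 (Aim 6) sets three windows for each assessment. For the end of FR, the planned date is listed as "3) on the last day of FR", and this is the narrow window. Modest flexibility runs from at most two treatment days before FR ends to "7 calendar days after end of FR". Moderate flexibility starts at the same point and runs to "30 calendar days after end of FR". The analysis codes one indicator per observation, inside the narrow window or not, and then: "We will use an interaction term of this indicator with the intervention to see if the intervention shows a differential effect".

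Section 10.1 (Design, repeated under Randomization) states that "the standard FR group will be offered the option of IM following completion of the FR program". Table 2 gives this course as three weeks, at the patient's option. No start date, deadline or expected uptake is stated. The column layout of Table 2 is broken in the available text, so the reading that only controls receive the offer rests on the prose of section 10.1.

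Section 10.12 says that the subject data sheets hold "starting and ending dates of participation in standard care, integrative modalities care and functional restoration" (item 2). It also says that contact hours by discipline, including chiropractic, acupuncture, yoga and massage, are tracked for up to six months after therapy (item 9). Nothing in Aim 6 mentions post-FR IM.

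**The concern.** The windows are defined by the calendar alone. A control assessed late can already have had some or all of the treatment under study and still be counted as an end-of-FR observation. A control assessed on the last day of FR cannot. Patients in the IM arm are offered no corresponding course after FR. At this time point, then, being outside the narrow window can mean something different in the two arms, and a timing-by-arm interaction picks up exactly that kind of difference.

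Aim 6 is meant to tell designers of future pragmatic trials how much slack in assessment dates is acceptable. If part of the interaction is crossover, the aim could report that late assessment erodes a treatment effect when what changed was the treatment received by controls.

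**Working it through.** **Inputs.** The course lasts 3 weeks = 21 days (section 10.1, Table 2). The upper window limits *w* are 0 days (narrow), 7 days (modest) and 30 days (moderate) after FR ends (section 11.3, Aim 6). The start day *s* of post-FR IM is not stated, so it is varied.

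**Room for the course.** 30 − 21 = 9 days to spare in the moderate window. In the modest window, 7/21 = 33% of the course fits at most. On Table 2's weekly schedule that is two chiropractic, two acupuncture and one yoga session.

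**Largest fraction of the course received by day *w*:** min(21, max(0, *w* − *s*)) / 21.

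| Start day *s* | Narrow, *w* = 0 | Modest, *w* = 7 | Moderate, *w* = 30 |
|---|---|---|---|
| 0 | 0 | 0.33 | 1.00 |
| 3 | 0 | 0.19 | 1.00 |
| 9 | 0 | 0 | 1.00 |
| 14 | 0 | 0 | 0.76 |
| 21 | 0 | 0 | 0.43 |

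These are maxima, for a score taken on the last permitted day. A full course needs a start by day 9 and a score at least 21 days after that start. If IM starts on the day FR ends, only scores from days 21 to 30 follow a complete course. With scores spread evenly over days 1 to 30 (an assumption), the mean fraction received is 0.67 for a start on day 0, 0.37 for day 9 and 0.22 for day 14.

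**Effect on the interaction at the end of FR.** Let *D* be the arm difference on the last day of FR, *t* the true change in that difference from assessing late, *u* the share of off-window controls who take IM, *f* the mean fraction of the course they have received, and *δ* the effect of a full post-FR course on a control's score. If benefit is proportional to the fraction received, the off-window arm difference is *D* + *t* − *u·f·δ*. The interaction, off-window minus narrow, is *t* − *u·f·δ*. The plan has no term that separates the two parts.

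**Range, with every value of *u* and *f* assumed:**
- *u* = 0.25, *f* = 0.10: 0.25 × 0.10 = 0.025 of *δ*
- *u* = 0.5, *f* = 0.5: 0.5 × 0.5 = 0.25 of *δ*
- *u* = 1, *f* = 1: 1.0 of *δ*

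**Pooling.** Aim 6 does not say whether the interaction is fitted by time point or across all five. Post-FR IM cannot affect the two assessments before FR. At 3 and 6 months, narrow scores can follow IM too. With equal weights, and equal exposure of narrow and off-window scores at 3 and 6 months, the shift is one fifth of the figures above: 0.005, 0.05 and 0.20 of *δ*.

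**The case against.** The strongest case against is that this is a corner of a methodological aim. Off-window end-of-FR scores also include those taken up to two treatment days before FR ends and those from the first week after it, with little or no exposure. The plan says only that some controls may be interested in IM. It attributes off-schedule follow-up to subjects being unavailable, and a patient who cannot attend an assessment may be unlikely to attend several IM sessions a week. All of this limits the size of the problem. It does not remove it, because no rule prevents exposed scores from entering and only one arm is offered the course. Analysis by randomised arm does not resolve it either: it fixes the arm label but leaves timing and crossover mixed within the timing indicator.

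A reader might infer that late scores and the interaction measure crossover instead of timing. The documents do not support that. Only one of the five time points has this asymmetry, and complete replacement of the timing component needs extreme values of *u* and *f*.

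A reader might also multiply a guessed uptake by the full treatment effect and quote the result as the loss. No uptake is stated. Aim 1 concerns IM given before FR, and no effect of IM given after FR is stated anywhere.

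Finally, a reader might extend the point to Aim 1. The flexible windows appear only as comparison sets in Aim 6, and the primary comparison is at three months.

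**Conclusion.** The concern holds in a limited form. At the end-of-FR time point, the narrow-by-intervention interaction partly confounds assessment timing with IM received by controls. The direction follows if post-FR IM is beneficial: late arm differences shrink, and the shrinkage is credited to timing. Exposure is zero in the narrow window, at most one third of the course in the modest window, and up to the whole course in the moderate window if it starts by day 9.

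The size cannot be stated from the documents. The range in the working rests on assumed uptake, assumed exposure and a proportional effect, and shows only that the shift could be trivial or material. Pooling over five time points dilutes it. The three-month primary comparison does not depend on this window. Optional IM after FR could affect that comparison separately, but that is a different question.

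**What to change.** In Aim 6, flag every end-of-FR score taken after the patient's first post-FR IM session. Then:

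- tabulate flagged scores by arm and by window (modest, moderate);
- report the end-of-FR interaction separately from the other time points;
- show that interaction with and without the flagged scores.

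The IM dates on the subject data sheets or the tracked contact hours can supply the flag. Check first that the recorded IM dates cover the optional post-FR course, since section 10.12 does not say so. Derive the flag before the merged data are de-identified, because dates may not reach the analysts afterwards.

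The cost is a little more analysis and no new data collection. The version without flagged scores removes some controls according to a choice made after randomisation, and those who choose more treatment may differ from the rest. It can therefore introduce its own bias, so neither version should stand alone. The exclusion should not be carried into the intent-to-treat analysis of Aim 1.
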